Signs and symptoms of OSD are often non-specific to the ocular surface and caused by allergic, pro-inflammatory, or toxic conditions (Stewart et al., 2011). Ocular surface toxicity, especially to benzalkonium chloride (BAK) preservative, has been established and thoroughly discussed in the literature, which is why preservative-free treatment options are increasingly advocated, especially in patients already presenting with OSD (Stewart et al., 2011; Zhang et al., 2019). Performing a comprehensive tear film assessment in glaucoma patients may be beneficial and lead to a better understanding of the disease. To the best of our knowledge, no studies performed a full ocular surface assessment in glaucoma patients on topical treatment with IOP-lowering eye drops.

Research objectives and significance:

The main objective of the study is to investigate signs and symptoms of ocular surface disease in patients on topical glaucoma medications.

The main objective of the study is based on the following research questions:

1. What is the occurrence of signs and symptoms of ocular surface disease (OSD) in patients with primary open-angle glaucoma (POAG) who have been on treatment with IOP-lowering eye drops for at least three months?
2. Is the occurrence of signs and symptoms of OSD in patients with POAG related to added preservatives in the IOP-lowering eye drops?
3. Is the occurrence of signs and symptoms of OSD in patients with POAG modified by the active pharmacological substance in the IOP-lowering eye drops?

4. Is the occurrence of signs and symptoms of OSD in patients with POAG related to the duration of the treatment with the IOP-lowering eye drops?

Based on research questions 2-4, the following hypotheses were formulated:

1. In a sample of patients with POAG, who have been on treatment with IOP lowering eye drops for at least three months, the frequency of signs of OSD, defined as hyperosmolarity, reduced NIKBUT, ocular surface staining, or reduced Schirmer 1 test, is greater in patients that are on eye drops with preservatives compared with those that are not.
2. In a sample of patients with POAG, who have been on treatment with IOP lowering eye drops for at least three months, the frequency of symptoms of OSD, defined as OSDI index ≥ 13 or SPEED II values >5 , is greater in patients that are on eye drops with preservatives compared with those that are not.

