3. In a sample of patients with POAG, who have been on treatment with IOP lowering eye drops for at least three months, the frequency of signs of OSD, defined as hyperosmolarity, reduced NIKBUT, ocular surface staining, or reduced Schirmer 1 test is modified by the active pharmacological substance in the IOP-lowering eye drops.
4. In a sample of patients with POAG, who have been on treatment with IOP lowering eye drops for at least three months, the frequency of symptoms of OSD, defined as OSDI index ≥ 13 or SPEED II values >5 , is modified by the active pharmacological substance in the IOP-lowering eye drops.
5. In a sample of patients with POAG, who have been on treatment with IOP lowering eye drops for at least three months, the frequency of signs of OSD, defined as hyperosmolarity, reduced NIKBUT, ocular surface staining, or reduced Schirmer 1 test is related to the duration of the treatment with an IOP-lowering eye drop of a specific pharmacological category (prostaglandin analogs, beta-blocker, carbohydrase inhibitor or alfa-2-agonist).
6. In a sample of patients with POAG, who have been on treatment with IOP lowering eye drops for at least three months, the frequency of symptoms of OSD, defined as OSDI index ≥ 13 or SPEED II values >5 , is related to the duration of the treatment with an IOP-lowering eye drop of a specific pharmacological category (prostaglandin analogs, beta-blocker, carbohydrase inhibitor or alfa-2-agonist).

The secondary objective of this study is to investigate a relationship between compliance and signs and symptoms of the ocular surface disease.

The secondary objective of the study was based on the following research questions:

1. Is the occurrence of signs and symptoms of OSD in patients with POAG related to self-reported compliance to the treatment with the IOP lowering eye drops?
2. Is the occurrence of signs and symptoms of OSD in patients with POAG independently related to self-reported compliance to the treatment with the IOP lowering eye drops?

Based on these research questions, the following hypotheses were formulated:

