1. In a sample of patients with POAG who have been on treatment with IOP lowering eye drops for at least three months, the frequency of signs of OSD, defined as hyperosmolarity, reduced NIKBUT, ocular surface staining, or reduced Schirmer 1 test, is different in patients with self-reported poor compliance, defined as single dose skipped or forgotten more than once a week (Robin & Grover, 2011), compared with patients with good self-reported compliance.
2. In a sample of patients with POAG who have been on treatment with IOP lowering eye drops for at least three months, the frequency of symptoms of OSD, defined as OSDI index ≥ 13 or SPEED II values >5 , is different in patients with self-reported poor compliance, defined as single dose skipped or forgotten more than once a week, compared with patients with good self-reported compliance.

3. In a sample of patients with POAG who have been on treatment with IOP lowering eye drops for at least three months, the frequency of signs of OSD, defined as hyperosmolarity, reduced NIKBUT, ocular surface staining, or reduced Schirmer 1 test, is different in patients with self-reported poor compliance, defined as single dose skipped or forgotten more than once a week, compared with patients with good self-reported compliance, when adjusted for preservatives, pharmacological substance, and duration of treatment.
4. In a sample of patients with POAG who have been on treatment with IOP lowering eye drops for at least three months, the frequency of symptoms of OSD, defined as OSDI index ≥ 13 or SPEED II values >5 , is different in patients with self-reported poor compliance, defined as single dose skipped or forgotten more than once a week, compared with patients with good self-reported compliance, when adjusted for preservatives, pharmacological substance, and duration of treatment.

The results are expected to improve the understanding of the connection between glaucoma treatment with IOP-lowering eye drops and ocular surface disease. Acknowledgment of the problem may help to individualize treatment options for patients in agreement with personalized medicine. This could consequentially lead to the general improvement of patient life quality and treatment compliance that could also positively affect glaucoma treatment outcomes.

Study design:

This is a cross-sectional study with six months prospective data collection.

Study sample:

The target population is patients on topical treatment for POAG.

Study population:

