Recruitment of subjects will take place in the ophthalmologic practice of Ifocus Øyeklinikk in Haugesund, Norway. This study is a sub-study of an “Ocular Surface and glaucoma. A randomized study of IOP reducing eye drops versus surgical intervention” study (REK no. 253485), and the participants in this study will be recruited from subjects that have given their consent to participate in the main study. Patients who come for follow-up glaucoma controls with visual field examination in our clinic and meet all criteria for inclusion will be invited to participate in the study. Eligible patients will be given oral and written information about the study together with a consent form (Appendix 1). The recruited patients’ names will be replaced with unique randomized three-digit ID numbers to ensure the anonymity of the participants. The key list that links patients’ names with ID numbers will be deleted five years after the completion of the study. The aim is to recruit 30 subjects (60 eyes), which is a feasible number of subjects to perform a full ocular surface assessment on in the chosen timeframe of six months.

Variables:

Outcome variables:

OSD-related disability (The Ocular Surface Disease Index (OSDI)) is defined as an impairment caused by OSD that makes it more difficult for an individual to perform daily activities. Operationally, it is defined as the self-reported frequency of ocular symptoms (3 items), visual function (6 items), and environmental triggers (3 items) measured by means of The Ocular Surface Disease Index (Schiffman, Christianson, Jacobsen, Hirsch, & Reis, 2000), which is a validated questionnaire that has been proven to accurately differentiate between normal, mild to moderate, and severe dry eye disease. It measures the frequency of symptoms with one week recall period. The OSDI is registered in whole numbers on a numerical scale from 0 (0=no disability) to 100 (100=complete disability).

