
Analyses:

The results of the comprehensive tear film evaluation will be recorded in the patient journal system (Infodoc Plenario) used at the Ifocus Øyeklinikk, Haugesund, Norway. The data collected with the Oculus Keratograph 5M by OCULUS, Inc. will be stored in a separate database called Oculus Patient Data Management. Once measurements are performed, data related to the study will be transferred from the patient journal to a data registration form (Appendix 4). The names of the patients will be replaced with ID numbers. All data will be transferred to and organized in a database (Excel, Microsoft Inc.). To identify empty cells or unrealistic values, an algorithm in Excel will flag the cells in question. A quality-assured version of the database will constitute the basis for statistical analyses. For variables measured on a numerical scale, these summaries will include the sample size, as well as the mean, standard deviation, median, minimum, and maximum. For variables measured on a categorical scale, summaries will provide the number and percentage of subjects who provided each score. Preliminary considerations of the data will include the investigation as to whether any transformation (i.e., logarithmic) should be applied prior to the statistical analyses. For categorical data, the sparseness of the data across categories will be considered, and the combination of categories prior to statistical analysis will be applied where deemed appropriate. For variables measured on a continuous scale, the statistical significance of the difference

between groups will be investigated using an Analysis of Variance (ANOVA) with appropriate post-hoc testing. For variables measured on an ordinal categorical scale, the Kruskal-Wallis signed-rank test will be employed. Questionnaire data will be analyzed using current standards. The statistical analyses will be performed using SPSS version 24. All statistical tests of hypotheses will employ a level of significance of $\alpha=0.05$. Odds ratios with 95% confidence intervals may also be used.

Project management and organization:

Principal investigator: [name]

Project manager: [name]

Resources, equipment, and physical facilities:

All equipment is available in the ophthalmic practice Ifocus Øyeklinikk in Haugesund, Norway, where the study will take place:

- The TearLab Osmolality System by TearLab Corporations.
- The Oculus Keratograph 5M by OCULUS, Inc.

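### Ten hypotheses are each tested at 0.05 in 30 patients, with none designated primary, none labelled exploratory and no control of error across them

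*Protocol*

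**What the plan says.** Under Research objectives and significance, the protocol states a main objective: "The main objective of the study is to investigate signs and symptoms of ocular surface disease in patients on topical glaucoma medications". Four research questions follow. The first, on occurrence, is descriptive. The other three lead to hypotheses: "Based on research questions 2-4, the following hypotheses were formulated". There are six, one for signs and one for symptoms for each of preservative, active substance and duration of treatment.

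A secondary objective on compliance is introduced in the same way: "Based on these research questions, the following hypotheses were formulated". It has four hypotheses, again for signs and symptoms, first unadjusted and then adjusted for preservative, substance and duration. Each states that the frequency "is different in patients with self-reported poor compliance, defined as single dose skipped or forgotten more than once a week" compared with patients reporting good compliance.

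The first Recruitment section sets the size: "The aim is to recruit 30 subjects (60 eyes), which is a feasible number of subjects". No effect size, power or precision target is given.

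The Analyses section plans ANOVA for continuous variables, with post-hoc testing, and a Kruskal-Wallis test for ordinal ones. It then says: "All statistical tests of hypotheses will employ a level of significance of" 0.05. Categorical variables are summarised as counts and percentages. Odds ratios with 95% confidence intervals are mentioned as an option.

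**The concern.** When ten hypotheses carry the same rank and the same threshold, the protocol does not say which result answers the study's question. After the data are seen, whichever hypothesis falls below 0.05 can be presented as confirmed, and the reader cannot tell whether it was the one that mattered beforehand. The post-hoc testing attached to the ANOVA does not help, because it works within one comparison of several groups and not across hypotheses or outcomes.

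The small sample adds to this. A real but moderate association may well be missed, so a non-significant result says little. The occurrence question, which 30 patients can answer to a known precision, has no stated confidence interval. The results are meant for journal submission and are expected to help individualise treatment, so the standing of each result matters.

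**Working it through.** **The plan's own figures.** The protocol derives neither the 0.05 (a chosen level) nor the 30 (feasibility) from other inputs, so there is no calculation to reproduce.

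**Inputs from the protocol.** Six main hypotheses, four secondary hypotheses, 0.05 for each, 30 patients.

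**False positives if all nulls are true and the tests are independent.** The chance of at least one is 1 − (1 − 0.05)^k.
- Six main hypotheses: 1 − 0.95^6 = 0.265, about 26%.
- All ten: 1 − 0.95^10 = 0.401, about 40%.
- The limit under any form of dependence is k × 0.05, that is 0.30 and 0.50.

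**Allowing for correlation.** The ten tests share two composite endpoints, and two of the compliance hypotheses are adjusted forms of the other two. A null simulation used 30 patients and 1,000 runs per setting. Its assumptions, none from the protocol, were: group sizes of 15/15 for preservative, 16/6/4/4 for substance and 10/20 for compliance; composites treated as mean scores; and equal correlation among outcomes. The chance of at least one false positive among the ten was:

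| Assumed correlation | At least one of ten |
|---|---|
| 0 | 38% |
| 0.3 | 32% |
| 0.6 | 27% |

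The simulation error is about 1.5 percentage points: √(0.3 × 0.7 / 1000) = 0.014.

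**Single outcome measures.** Twelve outcome variables are defined, and six of them are components of the two composites. If single measures are also tested, the chance rises further, but the protocol does not fix how many such tests there will be.

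**Power, for illustration only.** Assume 15 versus 15 patients, assumed rates and a two-sided Fisher's exact test, which the protocol does not name. Exact enumeration gives 10% power for 60% versus 40%, and 43% for 70% versus 30%.

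**Effect of a Bonferroni correction instead.** The level would be 0.05/10 = 0.005. By a normal approximation with an assumed 15/15 split and 40% versus 70%, power falls from 37% at 0.05 to 11% at 0.005.

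**Precision of the occurrence estimate.** Wilson interval for 15 of 30, with p = 0.5, n = 30, z = 1.96:
- Half-width = z × √(p(1 − p)/n + z²/(4n²)) / (1 + z²/n) = 1.96 × √(0.00833 + 0.00107) / 1.128 = 0.168.
- Interval: 0.332 to 0.668, or 33% to 67%.

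**The case against.** Several points on the other side stand.

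- **The objectives are ranked.** The compliance hypotheses are already secondary, and occurrence already comes first among the research questions. What is missing is a primary hypothesis among the six main ones.
- **0.05 is a per-test level.** A reader might infer that the protocol presents it as the error rate of the whole study, and so misstates it. It does not.
- **A chance finding is not shown to be likely.** A reader might infer this from the ten hypotheses and twelve outcomes. For the ten hypotheses the figure is about 27% to 40%, below one half. A conservative test lowers it: Fisher's exact test at 15 versus 15 has a true size of about 1.7% at a common rate of 50%, so ten independent tests of that kind would give about 15%. Not all ten are two-by-two comparisons, so this is only illustrative.
- **The number of tests cannot be had by multiplication.** Crossing twelve outcomes with four predictors gives 48 tests, but the protocol plans no such grid. It gives methods by variable type, ties 0.05 to tests of hypotheses, and states no between-group test that suits duration in months. Adding ten and twelve would count the six composite components twice.
- **A separate analysis plan may exist.** A detailed multiplicity procedure or interval method could sit there.
- **Scale and openness.** This is a Master thesis project whose size is openly justified by feasibility, and nothing in it says that non-significance will be read as absence of a relation.

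These points narrow the concern but do not remove it. Choosing the primary question belongs in the protocol, and the protocol does fix a rule: ten hypotheses, one threshold, none set apart.

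**Conclusion.** The concern holds in a limited form. The protocol tests six co-equal main hypotheses and four secondary ones at 0.05 each, with no designated primary hypothesis, no exploratory label and no control across them. If all nulls were true, the chance of at least one false positive would be about 26% for the six and 40% for the ten under independence with exact 5% tests, and about 27% to 32% for the ten under assumed correlations of 0.6 to 0.3. It would be higher if single measures were tested as well, by an amount that the protocol does not allow one to state. The correlations, group sizes and event rates are all assumptions, and the power figures are illustrative. This is a change that should be made. It affects how results may be claimed, not whether the study can be run.

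**What to change.** In Research objectives and significance, and again in Analyses, state that:

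1. Research question 1 (occurrence) is the main estimate, reported per patient with a Wilson or exact 95% confidence interval.
2. One hypothesis is primary and tested at 0.05. The choice is the investigators'; main hypothesis 1, preserved against preservative-free drops, is one candidate. If it is chosen, its cut-offs for the signs should be written into it.
3. The other nine hypotheses and the single outcome measures are exploratory, reported as effect estimates with 95% confidence intervals. Nominal p-values are not read as confirmation, and non-significance is not read as absence of a relation.

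The cost is two or three sentences and no added patients. The downside is that fewer results can be called significant. Naming a primary hypothesis does not raise its power, which may remain low with 30 patients. It does avoid the further loss that a correction over all ten would bring.
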